10. DEMOGRAPHIC AND OTHER SCREENING CHARACTERISTICS

Demographic data and other baseline characteristics (including screening disease characteristics) will be presented for all analysis sets (RND, SAF, FAS, PK), by treatment groups, if the analysis sets differ to each other. If these are the same, as is expected for Part A, the presentation will be limited to just the RND analysis set, or to those that are

Document: Z:\RPL554\AZA40375\Biostatistics\Documentation\SAP\Verona RPL554-DP-201 SAP v1.0 – Part A

Author: [name]

Version Number: 1.0

Version Date: [19DEC2018]

Template No.: CS_TP_BS016 Revision 5

Reference: CS_WI_BS005

Effective Date: 01Apr2018

Copyright © 2009, 2010, 2012, 2016, 2018 IQVIA. All rights reserved. The contents of this document are confidential and proprietary to IQVIA Holdings Inc. and its subsidiaries. Unauthorized use, disclosure or reproduction is strictly prohibited.

different. No statistical testing will be carried out for demographic or other baseline characteristics. The following demographic and other baseline characteristics will be reported for Part A:

- Age (years)
- Sex
- Childbearing potential
- Race
- Ethnicity
- Height (inches)
- Weight (pounds)
- BMI (kg/m^2)
- Pre (prior to dosing at baseline)/post (post dosing at baseline) bronchodilator FEV₁ (both in liters and in percentage of predicted normal)
- Post-bronchodilator FEV₁/FVC
- FEV₁ reversibility test (mL and %)

10.1. DERIVATIONS

- Age (years) = (Informed consent date – date of birth)
- BMI (kg/m^2) = weight (kg)/ height (m)²

Demographic and other screening characteristics recorded on the eCRF will be used as is on the eCRF, without any derivations or adjustments.

11. SURGICAL, MEDICAL AND CHRONIC OBSTRUCTIVE PULMONARY DISEASE/SMOKING HISTORY

Surgical and Medical History information will be presented in table summaries and listings, for the RND analysis

Document: Z:\RPL554\AZA40375\Biostatistics\Documentation\SAP\Verona RPL554-DP-201 SAP v1.0 – Part A

Author: [name]

Version Number: 1.0

Version Date: [19DEC2018]

Template No.: CS_TP_BS016 Revision 5

Reference: CS_WI_BS005

Effective Date: 01Apr2018

Copyright © 2009, 2010, 2012, 2016, 2018 IQVIA. All rights reserved. The contents of this document are confidential and proprietary to IQVIA Holdings Inc. and its subsidiaries. Unauthorized use, disclosure or reproduction is strictly prohibited.

set.

- Surgical History will be coded by Medical Dictionary for Regulatory Activities (MedDRA) dictionary using the version specified in the data management plan.
 - Surgical History conditions are defined as those conditions which stop prior to or at Screening.
 - Data captured on the Surgical Procedure History page of the eCRF will be presented by SOC (System Organ Class) and PT (Preferred Term).
- Medical History will be coded by MedDRA dictionary using the version specified in the data management plan.
 - Medical History conditions are defined as those conditions which stop prior to or at Screening.
 - Data captured on the Medical History page of the eCRF will be presented by SOC and PT.
- COPD/Smoking History data captured on the COPD and Smoking History page of the eCRF will be presented for the RND analysis set.
 - COPD history (Duration of COPD [calculated relative to date of first diagnosis {Randomization date – first COPD diagnosis date}], date of most recent exacerbation, known to have chronic bronchitis/emphysema)
 - Smoking history (current or former smoker, number of packs per day, number of years smoking and number of pack-years [calculated as number of packs per day x number of years smoking])

12. MEDICATIONS

Medications will be coded using the World Health Organization – Drug Dictionary (WHO-DD) version specified in the data management plan and will be presented in a listing by Anatomical Therapeutic Chemical (ATC) (the 1st level of the ATC code) and PT for the RND analysis set. Certain medications (or a special grouping of medications) will be classified in a list during the study and signed-off prior to lock by a medical advisor. As this list, may change prior to sign-off they will not be defined in this section of the SAP. Potential medications include, but are not limited to, inhaled corticosteroids (ICS), LAMAs (long-acting muscarinic antagonists), LABAs (long-acting beta2-agonists) etc.

Document: Z:\RPL554\AZA40375\Biostatistics\Documentation\SAP\Verona RPL554-DP-201 SAP v1.0 – Part A

Author: [name]

Version Number: 1.0

Version Date: [19DEC2018]

Template No.: CS_TP_BS016 Revision 5

Reference: CS_WI_BS005

Effective Date: 01Apr2018

Copyright © 2009, 2010, 2012, 2016, 2018 IQVIA. All rights reserved. The contents of this document are confidential and proprietary to IQVIA Holdings Inc. and its subsidiaries. Unauthorized use, disclosure or reproduction is strictly prohibited.

See [Appendix 2](#) for handling of partial dates for medications, in the case where it is not possible to define a medication as prior, concomitant, or post treatment, the medication will be classified by the worst case; i.e. concomitant.

- ‘Prior’ medications are medications which started and stopped in the 3 months prior to the single dose of study medication and are recorded at Screening.
- ‘Concomitant’ medications are medications which:
 - Had an onset date on or after the single dose of study medication.
 - AND ended on or after the date of single dose of medication or were ongoing at the end of Part A.
 - A patient can report more than 1 concomitant medication with the same PT.

Prior and concomitant medications will be presented in a listing only, by treatment group.

Rescue medications will be recorded on the Rescue Medication/Rescue Medication Canister Collection/Rescue Medication Canister Dispensed/Rescue Medication Canister Weight pages of the eCRF. These are short acting bronchodilators and will be sourced by the study center and dispensed at the Screening visit and end of Part A (Day 2). Rescue medication used during study visits will be documented on the eCRF pages. Protocol procedures must continue even if rescue medication has been taken. Salbutamol/albuterol is to be used for primary rescue use.

Rescue medications used during study visits (by recording the time it was dispensed and collected) and the amount taken between Day 1 and Day 2 (by recording the weight of the canisters), will be presented in a listing for the RND analysis set.

13. STUDY MEDICATION EXPOSURE

Date and time of exposure to the single dose of study medication and the date of completion/discontinuation will be presented in a listing for the SAF analysis set. Duration of exposure will not be calculated as this is expected to be one day for all patients in Part A. The information to be listed will be taken from the Drug Exposure and Disposition eCRF pages.

Document: Z:\RPL554\AZA40375\Biostatistics\Documentation\SAP\Verona RPL554-DP-201 SAP v1.0 – Part A

Author: [name]

Version Number: 1.0

Version Date: [19DEC2018]

Template No.: CS_TP_BS016 Revision 5

Reference: CS_WI_BS005

Effective Date: 01Apr2018

Copyright © 2009, 2010, 2012, 2016, 2018 IQVIA. All rights reserved. The contents of this document are confidential and proprietary to IQVIA Holdings Inc. and its subsidiaries. Unauthorized use, disclosure or reproduction is strictly prohibited.

14. STUDY MEDICATION COMPLIANCE

All administration of study treatment will be done at the clinic under supervision of the study staff; therefore, no formal analysis of compliance will be performed.

15. EFFICACY OUTCOMES

15.1. PRIMARY EFFICACY

15.1.1. PRIMARY EFFICACY VARIABLE(S) & DERIVATION(S)

- Not applicable – The primary endpoint of Part A will be described in [Section 17](#).

15.1.2. MISSING DATA METHODS FOR PRIMARY EFFICACY VARIABLE(S)

Not applicable.

15.1.3. PRIMARY ANALYSIS OF PRIMARY EFFICACY VARIABLE(S)

Not applicable.

15.2. SECONDARY EFFICACY

The secondary efficacy analyses will be performed for the FAS.

Document: Z:\RPL554\AZA40375\Biostatistics\Documentation\SAP\Verona RPL554-DP-201 SAP v1.0 – Part A

Author: [name]

Version Number: 1.0

Version Date: [19DEC2018]

Template No.: CS_TP_BS016 Revision 5

Reference: CS_WI_BS005

Effective Date: 01Apr2018

Copyright © 2009, 2010, 2012, 2016, 2018 IQVIA. All rights reserved. The contents of this document are confidential and proprietary to IQVIA Holdings Inc. and its subsidiaries. Unauthorized use, disclosure or reproduction is strictly prohibited.

15.2.1. SECONDARY EFFICACY VARIABLES & DERIVATIONS

15.2.1.1. Change in baseline in average FEV₁ of AUC_{0-4h} (Average FEV₁ over 4 hours) after single dose (Secondary variable 1)

Average FEV₁ after single dose is defined as the AUC_{0-4h} FEV₁ collected, divided by the length of the time (in hours). AUC_{0-4h} FEV₁ is derived using the following formula:

$$AUC = \frac{1}{2}(t_1 - t_0)(y_1 + y_0) + \frac{1}{2}(t_2 - t_1)(y_2 + y_1) + \dots + \frac{1}{2}(t_i - t_{i-1})(y_i + y_{i+1})$$

where i are the number of intervals, t_i are the time values or time intervals (in actual hours) between assessments and y_i the FEV₁ values at t_i . The AUC result will then be divided by the actual time (the time elapsed since dosing, until the time of assessment) at 4-hour assessment (as this can occur ± 10 minutes) to obtain the average FEV₁. For analysis purposes, it will be assumed that the pre-dose value (immediately pre-dose) occurred at time 0 when computing PD parameters. If a patient misses hour 2 and 4 then the AUC₀₋₄ is set to missing.

Descriptive statistics (see [Appendix 1](#) [Programming conventions for outputs]) for AUC₀₋₄ will be presented for all patients assigned to FAS, at each assessment and change from baseline at each assessment as relevant. All summaries will be presented for each treatment group. In addition, a figure (bar graph) representing mean change from baseline FEV₁ to FEV₁ AUC₀₋₄ by treatment will be presented, including the standard error of the mean.

Change from baseline FEV₁ to FEV₁ AUC₀₋₄ will be derived to test the hypothesis described in [Section 15.2.3](#) with baseline defined as the average of the FEV₁ pre-dose assessments (-60 minutes and -5 minutes) collected.

15.2.1.2. Change in baseline in average FEV₁ AUC_{0-12h} (Average FEV₁ over 12 hours) after single dose (Secondary variable 2)

AUC_{0-12h} FEV₁ after single dose is defined and derived similarly to secondary endpoint above (see [Section 15.2.1.1](#)), but over 12-hours post-dose. If patient misses hours 11.5 and 12 then the AUC_{0-12h} is set to missing.

Document: Z:\RPL554\AZA40375\Biostatistics\Documentation\SAP\Verona RPL554-DP-201 SAP v1.0 – Part A

Author: [name]

Version Number: 1.0

Version Date: [19DEC2018]

Template No.: CS_TP_BS016 Revision 5

Reference: CS_WI_BS005

Effective Date: 01Apr2018

Copyright © 2009, 2010, 2012, 2016, 2018 IQVIA. All rights reserved. The contents of this document are confidential and proprietary to IQVIA Holdings Inc. and its subsidiaries. Unauthorized use, disclosure or reproduction is strictly prohibited.

15.2.1.3. Change from baseline in peak FEV₁ (measured in first 4 hours) after single dose (Secondary variable 3)

Peak FEV₁ is measured in the first 4 hours after single dose. It is collected on the Spirometry Study measurements eCRF page.

Three acceptable readings are performed at each of the timepoints in first 4 hours after the single dose (5, 15 and 30 minutes and 1, 1.5, 2 and 4 hours) and the highest of the 3 is used for analysis purposes. Hence peak FEV₁ is derived as the highest of all these readings.

Descriptive statistics (see [Appendix 1](#) [Programming conventions for outputs]) for peak FEV₁ will be presented for all patients assigned to FAS, at each assessment and change from baseline as relevant. All summaries will be presented for each treatment group. In addition, a figure (bar graph) representing mean change from baseline FEV₁ to peak FEV₁ by treatment will be presented, including the standard error of the mean. A figure also displaying the mean change over time on Day 1 will be presented.

Change from baseline FEV₁ to peak FEV₁ (over 4 hours) will be derived to test the hypothesis described in [Section 15.2.3](#) with baseline defined as the average of the FEV₁ pre-dose assessments (-60 minutes and -5 minutes) collected.

15.2.2. MISSING DATA METHODS FOR SECONDARY EFFICACY VARIABLE(S)

No imputation will be applied.

15.2.3. ANALYSIS OF SECONDARY EFFICACY VARIABLES

The secondary variables will be analyzed by comparing the RPL554 treatment groups to each other and placebo by rejecting the null hypothesis described below at significance level $\alpha=0.05$ level (2-sided):

Document: Z:\RPL554\AZA40375\Biostatistics\Documentation\SAP\Verona RPL554-DP-201 SAP v1.0 – Part A

Author: [name]

Version Number: 1.0

Version Date: [19DEC2018]

Template No.: CS_TP_BS016 Revision 5

Reference: CS_WI_BS005

Effective Date: 01Apr2018

Copyright © 2009, 2010, 2012, 2016, 2018 IQVIA. All rights reserved. The contents of this document are confidential and proprietary to IQVIA Holdings Inc. and its subsidiaries. Unauthorized use, disclosure or reproduction is strictly prohibited.

$$H_0: \mu_j = \mu_0 \text{ versus } H_1: \mu_j \neq \mu_0$$

where μ_j and μ_0 are the mean change from Baseline for each parameter (Peak FEV₁, AUC_{0-4h} and AUC_{0-12h}) after single dose for each respective dose of RPL554 and placebo.

ANCOVA analyses will be implemented using the SAS® procedure MIXED as follows:

```
PROC MIXED DATA = ...;
  CLASS TREATMENT;
  MODEL CHG = TREATMENT BASELINE;
  LSMEANS TREATMENT / CL DIFF;
RUN;
```

where CHG = difference in log (parameter) – log (baseline parameter) i.e. log (parameter / baseline parameter)

TREATMENT = treatment group (Respective dose of RPL554, 150µg, 500µg, 1500µg, 3000µg and 6000µg and placebo)

BASELINE = log (baseline parameter)

The primary comparison will be the contrast (difference in least squares mean [LSMEAN]) between 6000µg RPL554 and placebo. The parameter value and its baseline will be log-transformed prior to analysis using natural logarithm. The difference between the two (log [parameter] – log [baseline parameter]) equals log (parameter / baseline parameter). The covariate, baseline parameter, will also be log transformed. Therefore, the LSMEAN statement between treatments in the above PROC MIXED will provide the log of the contrasts. Prior to presentations, the antilog of these point estimates and associated 95% confidence intervals will be performed, giving ratios of geometric means on the linear scale. The 2-sided p-value for the exponential (exp)least squares mean, exp(LSM), ratio between each of the 2 treatment groups and placebo will be reported.

Summary statistics for each parameter (Peak FEV₁, AUC_{0-4h} and AUC_{0-12h}) will be presented for baseline, at point of interest and change from baseline by treatment group on patients with both assessments, on the original scale.

Document: Z:\RPL554\AZA40375\Biostatistics\Documentation\SAP\Verona RPL554-DP-201 SAP v1.0 – Part A

Author: [name]

Version Number: 1.0

Version Date: [19DEC2018]

Template No.: CS_TP_BS016 Revision 5

Reference: CS_WI_BS005

Effective Date: 01Apr2018

Copyright © 2009, 2010, 2012, 2016, 2018 IQVIA. All rights reserved. The contents of this document are confidential and proprietary to IQVIA Holdings Inc. and its subsidiaries. Unauthorized use, disclosure or reproduction is strictly prohibited.

16. SAFETY OUTCOMES

All outputs for safety outcomes will be based on the SAF.

There will be no statistical comparisons between the treatment groups for safety data, unless otherwise specified with the relevant section.

16.1. ADVERSE EVENTS

Adverse Events (AEs) will be coded by MedDRA dictionary using the version specified in the data management plan.

Treatment emergent adverse events (TEAEs) are defined as AEs that started or worsened in severity on or after the single dose of study medication, based on the investigator assessment of severity. TEAEs will be assigned to treatment groups based on actual treatment received.

See [Appendix 2](#) for handling of partial dates for AEs. In the case where it is not possible to define an AE as treatment emergent or not, the AE will be classified by the worst case; i.e. treatment emergent.

An overall summary of number of patients within each of the categories described in the sub-section below, will be provided as specified in the templates.

Listings will include TEAEs and Non-TEAEs.

16.1.1. ALL TEAES

Incidence of TEAEs will be presented by System Organ Class (SOC) and Preferred Term (PT) and broken down further by maximum severity and relationship to study medication.

Document: Z:\RPL554\AZA40375\Biostatistics\Documentation\SAP\Verona RPL554-DP-201 SAP v1.0 – Part A

Author: [name]

Version Number: 1.0

Version Date: [19DEC2018]

Template No.: CS_TP_BS016 Revision 5

Reference: CS_WI_BS005

Effective Date: 01Apr2018

Copyright © 2009, 2010, 2012, 2016, 2018 IQVIA. All rights reserved. The contents of this document are confidential and proprietary to IQVIA Holdings Inc. and its subsidiaries. Unauthorized use, disclosure or reproduction is strictly prohibited.

16.1.1.1. Severity

Severity is classed as mild/ moderate/ severe (increasing severity). TEAEs starting after the single dose of study medication with a missing severity will be classified as severe. If a patient reports a TEAE more than once within that SOC/ PT, the AE with the worst-case severity will be used in the corresponding severity summaries.

16.1.1.2. Relationship to Study Medication

Relationship, as indicated by the Investigator, is classed as “yes” or “no”. A related TEAE is defined as a TEAE with a relationship to study medication as “yes”. TEAEs with a missing relationship to study medication will be regarded as relationship = “yes” to study medication. If a patient reports the same AE more than once within that SOC/ PT, the AE with the worst-case relationship to study medication will be used in the corresponding relationship summaries.

16.1.2. TEAES LEADING TO DISCONTINUATION OF STUDY

TEAEs leading to discontinuation from the study will be identified by using the question “Did the AE cause the Patient to discontinue from the study?” from the AE page of the eCRF.

For TEAEs leading to discontinuation from the study, summaries of incidence rates (frequencies and percentages) by SOC and PT will be prepared.

16.1.3. SERIOUS ADVERSE EVENTS

Serious adverse events (SAEs) are those events recorded as “Serious” on the Adverse Events page of the eCRF. A summary of serious TEAEs by SOC and PT will be prepared, similarly to [Section 16.1.1](#) and [Section 16.1.2](#).

16.1.4. ADVERSE EVENTS LEADING TO DEATH

TEAEs leading to Death are those events which are recorded as “Death” on the Adverse Events page of the eCRF. A

Document: Z:\RPL554\AZA40375\Biostatistics\Documentation\SAP\Verona RPL554-DP-201 SAP v1.0 – Part A

Author: [name]

Version Number: 1.0

Version Date: [19DEC2018]

Template No.: CS_TP_BS016 Revision 5

Reference: CS_WI_BS005

Effective Date: 01Apr2018

Copyright © 2009, 2010, 2012, 2016, 2018 IQVIA. All rights reserved. The contents of this document are confidential and proprietary to IQVIA Holdings Inc. and its subsidiaries. Unauthorized use, disclosure or reproduction is strictly prohibited.

summary of TEAEs leading to death by SOC and PT will be prepared.

16.2. LABORATORY EVALUATIONS

Results from the local laboratory will be included in the reporting of this study for hematology, blood chemistry, urinalysis and viral serology. A list of laboratory assessments to be included in the outputs is included in the protocol, Sections 7.4.3.1, 7.4.3.2, 7.4.3.3 and 7.1.4 for hematology, blood chemistry, urinalysis and viral serology, respectively. Presentations will use International system (SI) units.

Quantitative laboratory measurements reported as “< X”, i.e. below the lower limit of quantification (BLQ), or “> X”, i.e. above the upper limit of quantification (ULQ), will be converted to X for quantitative summaries, but will be presented as recorded, i.e. as “< X” or “> X” in the listings.

The following summaries will be provided for laboratory data:

- Actual results at Screening.
- Incidence of abnormal values at Screening according to normal range criteria
- Listing of all laboratory evaluations and abnormal values at Screening.

16.2.1. LABORATORY REFERENCE RANGES AND MARKEDLY ABNORMAL CRITERIA

Quantitative laboratory measurements will be compared with the relevant laboratory reference ranges in SI units and categorized as:

- Low: Below the lower limit of the laboratory reference range.
- Normal: Within the laboratory reference range (upper and lower limit included).
- High: Above the upper limit of the laboratory reference range.

In addition to the high and low quantitative laboratory assignments (as identified by means of the laboratory reference ranges), markedly abnormal quantitative blood chemistry values per the table below will also be identified by the Investigator.

Document: Z:\RPL554\AZA40375\Biostatistics\Documentation\SAP\Verona RPL554-DP-201 SAP v1.0 – Part A

Author: [name]

Version Number: 1.0

Version Date: [19DEC2018]

Template No.: CS_TP_BS016 Revision 5

Reference: CS_WI_BS005

Effective Date: 01Apr2018

Copyright © 2009, 2010, 2012, 2016, 2018 IQVIA. All rights reserved. The contents of this document are confidential and proprietary to IQVIA Holdings Inc. and its subsidiaries. Unauthorized use, disclosure or reproduction is strictly prohibited.

	Blood Chemistry – Markedly Abnormal Definition
Alanine Aminotransferase (ALT)	> 3 x ULN
Alkaline Phosphatase (ALP)	> 3 x ULN
Aspartate Aminotransferase (AST)	> 3 x ULN
Creatinine	> 221 µmol/L
Gamma Glutamyl Transferase (GGT)	> 3 x ULN
Bilirubin (TBL)	> 3 x ULN

ULN: Upper limit of normal. ALT: Alanine aminotransferase. AST: Aspartate aminotransferase.

ALP: Alkaline phosphatase. TBL: Total bilirubin.

16.3. ECG EVALUATIONS

Overall results from the local ECG (Electrocardiogram) lab will be included in the reporting of this study. The overall assessment of ECG parameters will be reported for this study:

- Normal
- Abnormal not Clinically Significant (ANCS)
- Abnormal Clinically Significant (ACS)
- Incomplete
- Uninterpretable

The following summaries will be provided for quantitative ECG data, for example heart rate:

- Actual assessments at screening, baseline (pre-dose of single dose) and each post-dose timepoint (1, 2, 4 and 8 hours)
- Change from Baseline at each post-dose timepoint assessment
- Shift of overall assessment baseline to post-dose timepoints according to Normal, ANCS and ACS overall

Document: Z:\RPL554\AZA40375\Biostatistics\Documentation\SAP\Verona RPL554-DP-201 SAP v1.0 – Part A

Author: [name]

Version Number: 1.0

Version Date: [19DEC2018]

Template No.: CS_TP_BS016 Revision 5

Reference: CS_WI_BS005

Effective Date: 01Apr2018

Copyright © 2009, 2010, 2012, 2016, 2018 IQVIA. All rights reserved. The contents of this document are confidential and proprietary to IQVIA Holdings Inc. and its subsidiaries. Unauthorized use, disclosure or reproduction is strictly prohibited.

assessment criteria

- Listing of all ECG evaluations and abnormal values

Peak heart rate after single dose is defined as the maximum value measured in the first 4 hours post-dose. Peak heart rate and change from baseline to peak will be summarized similarly to [Section 15.2.1.3](#), including the figure presentations. In addition, hypothesis testing as per Section [15.2.3](#), will be repeated for this endpoint.

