9.4.7 Safety

Safety data including laboratory safety tests, 12-lead ECG, vital signs and physical examinations, will be summarized by treatment group and timepoint of collection, when appropriate, for each of the two parts separately. For continuous variables, the change from baseline (pre-dose at each treatment period) to each post-dose time point will also be calculated and summarized. Data will further be illustrated by shift tables (showing changes from low/normal/high) and shift plots for selected time points. Separate listings will be generated of abnormal values occurring after the first dose of study treatment.

In Part A, change from baseline in peak pulse and peak heart rate will be compared between the treatments using analysis of covariance models with fixed factor treatment, and using the pre-dose baseline value as a covariate. In Part B, change from baseline in peak pulse will be compared between the treatments using analysis of covariance models with fixed factors for treatment, period and patient, and using the pre-dose Day 1 baseline value as a covariate. Additive model will be used for pulse and heart rate.

Coded adverse event terms will be presented by system organ class (SOC) and preferred term and summarized by treatment group for each part. Summary tables by treatment group with total number and number of patients with adverse events, SAEs, adverse events leading to discontinuation of study treatment, causally related adverse events and severe adverse events will be produced. Further SAEs, causally related adverse events and adverse events of each intensity will be summarized by SOC and preferred term.

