16.4. VITAL SIGNS

The following Vital Signs measurements will be reported for this study:

- Supine Systolic Blood Pressure (mmHg)
- Supine Diastolic Blood Pressure (mmHg)
- Supine Pulse Rate (bpm)

The following summaries will be provided for vital signs data:

- Actual assessments at screening, baseline (pre-dose of single dose) and each post-dose timepoint (1, 2, 4, 8, 12 and 24 hours [Day 2])
- Change from Baseline at each post-dose timepoint assessment
- Incidence of markedly abnormal values based on the criteria presented in the table below:

	Low	High
Systolic blood pressure (mmHg)	≤ 90 mmHg or decrease from Baseline of ≥ 20 mmHg	≥ 180 mmHg, or increase from Baseline of ≥ 20 mmHg
Diastolic blood pressure (mmHg)	≤ 50 mmHg or decrease from Baseline of ≥ 20 mmHg	≥ 105 mmHg, or increase from Baseline of ≥ 20 mmHg
Pulse rate (bpm)	≤ 50 bpm or decrease from Baseline of ≥ 20 bpm	≥ 110 bpm or increase from Baseline of ≥ 20 bpm

Document: Z:\RPL554\AZA40375\Biostatistics\Documentation\SAP\Verona RPL554-DP-201 SAP v1.0 – Part A

Author: [name]

Version Number: 1.0

Version Date: [19DEC2018]

Template No.: CS_TP_BS016 Revision 5

Reference: CS_WI_BS005

Effective Date: 01Apr2018

Copyright © 2009, 2010, 2012, 2016, 2018 IQVIA. All rights reserved. The contents of this document are confidential and proprietary to IQVIA Holdings Inc. and its subsidiaries. Unauthorized use, disclosure or reproduction is strictly prohibited.

Peak supine pulse rate after single dose is defined as the maximum value measured in the first 4 hours post-dose. Peak pulse rate and change from baseline to peak will be summarized similarly to [Section 15.2.1.3](#), including the figure presentations. In addition, hypothesis testing as per Section [15.2.3](#), will be repeated for these endpoints.

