16.4. VITAL SIGNS

The following Vital Signs measurements will be reported for this study:

- Supine Systolic Blood Pressure (mmHg)
- Supine Diastolic Blood Pressure (mmHg)
- Supine Pulse Rate (bpm)

The following summaries will be provided for vital signs data:

- Actual assessments at screening, baseline (pre-dose at each treatment period) and each post-dose time points, including end of study visit and overall (where overall is regardless of treatment period, day and timepoint to assess treatment group as a whole).
- Incidence of markedly abnormal values (number and percent) based on the criteria presented in the table below:

	Low	High
Systolic blood pressure (mmHg)	- ≤ 90 mmHg - Decrease from Baseline of ≥ 40 mmHg	- ≥ 180 mmHg - Increase from Baseline of ≥ 40 mmHg
Diastolic blood pressure (mmHg)	- ≤ 50 mmHg - Decrease from Baseline of ≥ 20 mmHg	- ≥ 110 mmHg - Increase from Baseline of ≥ 20 mmHg
Pulse rate (bpm)	- ≤ 50 bpm - Decrease from Baseline of ≥ 30 bpm	- ≥ 110 bpm - Increase from Baseline of ≥ 30 bpm

Peak supine pulse rate after study medication is defined as the maximum value measured in the first 4 hours post-dose. Peak pulse rate and change from baseline to peak on Day 1 and after morning dosing on Day 7 will be summarized similarly to [Section 15.1.3](#), including the figure presentation described in the same section. Treatment comparisons of change from baseline will be performed using an ANCOVA adjusting for treatment, treatment period and patient, and using pre-dose pulse rate as a covariate, like the hypothesis described in [Section 15.1.3](#). The model will be additive; therefore no log-transformation will be applied.

Document: Z:\RPL554\AZA40375\Biostatistics\Documentation\SAP\Verona RPL554-DP-201 SAP v2.0 – Part B

Author: [name] / [name]

Version Number: 2.0

Version Date: [08JUL2019]

Template No.: CS_TP_BS016 Revision 5

Reference: CS_WI_BS005

Effective Date: 01Apr2018

Copyright © 2009, 2010, 2012, 2016, 2018 IQVIA. All rights reserved. The contents of this document are confidential and proprietary to IQVIA Holdings Inc. and its subsidiaries. Unauthorized use, disclosure or reproduction is strictly prohibited.

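### The Part A SAP refers the tests of peak heart rate and peak pulse to a section that contains only the log-ratio FEV₁ model, while the protocol calls for additive models and the SAP declares no change.

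*SAP*

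**What the plan says.** **Protocol.** Section 9.4.7 sets the Part A analysis: "In Part A, change from baseline in peak pulse and peak heart rate will be compared between the treatments using analysis of covariance models", with treatment as fixed factor and the pre-dose value as covariate. It closes with "Additive model will be used for pulse and heart rate". The synopsis makes the same split, with multiplicative models for FEV₁ and additive ones for blood pressure, pulse rate and ECG heart rate. Change in peak pulse and peak heart rate is a Part A secondary endpoint (9.3.1.2), and these effects are named in the secondary safety objective (2.1.2).

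**Part A SAP.** For peak heart rate, 16.3 gives one inferential instruction: "In addition, hypothesis testing as per Section" 15.2.3 will be repeated. Section 16.4 says for peak pulse that the same testing "will be repeated for these endpoints". In 15.2.3 the response is defined by "where CHG = difference in log (parameter) – log (baseline parameter) i.e. log (parameter / baseline parameter"), and "The covariate, baseline parameter, will also be log transformed". Estimates and 95% limits are then antilogged, "giving ratios of geometric means on the linear scale". Section 3.3 reports no changes to the protocol analysis.

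**Part B SAP.** Section 16.4 also refers peak pulse to the log-scale FEV₁ section, but adds: "The model will be additive; therefore no log-transformation will be applied".

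**The concern.** A programmer who follows the cross-reference literally fits log(peak/baseline) on treatment and log(baseline), and reports a ratio for each dose against placebo. The protocol asks for a difference in bpm. The two documents therefore prescribe different tests and different effect measures for the same prespecified endpoint, and nothing in the SAP acknowledges it.

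The scale matters for interpretation. The SAP's own markedly abnormal limits for pulse in 16.4 are in bpm, and a geometric mean ratio cannot be read against them directly. Part B reports its peak pulse contrast additively, so the two parts' model-based pulse results would be in different units. Peak ECG heart rate after dosing is available only in Part A, because Part B records ECGs pre-dose only. Part B therefore cannot supply an adjusted bpm estimate for that variable. Part A safety data were also to be assessed when choosing the Part B doses (protocol synopsis).

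**Working it through.** The documents state no figure for these endpoints. The only sample-size calculation concerns Part B peak FEV₁ and has no bearing here. The check is mainly a comparison of texts, followed by two illustrations of size.

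**1. Side by side**

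| Element | Protocol 9.4.7 | Part A SAP 16.3/16.4 via 15.2.3 | Part B SAP 16.4 (peak pulse) |
|---|---|---|---|
| Response | change from baseline, additive | log(parameter/baseline) | change from baseline, no log |
| Covariate | pre-dose value | log(baseline) | pre-dose pulse rate |
| Reported effect | difference (implied by additive) | ratio of geometric means | difference (implied by additive) |
| Exception stated | not needed | none | yes |

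Section 15.2.3 contains no second, untransformed model to which the cross-reference could point.

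**2. What the change of scale does to the estimate**

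Assumed values, not in the documents: a drug effect of +8 bpm, and a peak without drug equal to baseline b. The ratio is (b + 8)/b. Both baselines used lie within the 50 to 90 bpm ECG range of inclusion criterion 4.

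- b = 55: 63/55 = 1.145
- b = 85: 93/85 = 1.094

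The same difference in bpm thus gives a ratio that depends on the baseline. Conversely, a ratio of 1.10 corresponds to 0.10 × 50 = 5 bpm at a baseline of 50, and 0.10 × 90 = 9 bpm at 90.

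**3. What it does to the test**

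This was simulated under assumptions that are not in the documents, except for six arms of six patients (protocol Table 1):

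- Baseline: normal, mean 70, SD 9, clipped to 50–90 bpm.
- Peak = 0.8 × baseline + 0.2 × 70 + 4 + normal error, with residual SD 6 or 8 bpm.
- A constant bpm effect in one active arm; two-sided α = 0.05; 3,000 runs per scenario.

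Each data set was analysed with both ANCOVAs.

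| True effect | Residual SD | Additive rejects | Log-ratio rejects | Verdicts differ |
|---|---|---|---|---|
| 0 bpm | 6 | 5.0% | 4.5% | 1.0% |
| 0 bpm | 8 | 5.1% | 5.0% | 1.0% |
| +5 bpm | 6 | 27.7% | 26.1% | 2.7% |
| +5 bpm | 8 | 18.0% | 16.3% | 3.0% |
| +10 bpm | 6 | 77.8% | 74.8% | 4.5% |
| +10 bpm | 8 | 53.2% | 48.5% | 5.7% |

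The type I error is about nominal under both models. The log model loses a little power when the true effect is additive, and the significance verdict differs in roughly 1% to 6% of runs. The main consequence is the unit of the estimate and its interval.

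**The case against.** The best counter-argument is Part A SAP 6.6. It defines change from baseline as an arithmetic difference for quantitative measurements in general, and lists log transformation for FEV₁ data only. Section 15.2.3 itself names its parameters as peak FEV₁ and the two FEV₁ AUCs. On that reading, repeating the testing of 15.2.3 means repeating the hypotheses and the ANCOVA structure, with the log step left behind.

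This stands as a reason for caution about intent, but it does not remove the conflict. Part B SAP 6.6 has the same two provisions, yet that SAP still states the additive exception for peak pulse in 16.4, and again for dyspnea in 15.3.3. The Part A SAP has no such sentence, so its prespecified test has two readings.

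Four stronger conclusions might be inferred, and the documents do not support them:

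- **That the Part A result was produced on the log scale.** The text shows a cross-reference that conflicts with the protocol, not what was run.
- **That no bpm results exist.** Values and changes at each timepoint, and change to peak, are summarised descriptively in bpm under 16.3 and 16.4.
- **That Part B is additive for both variables, so neither can be compared across parts.** Part B models peak pulse only. The mismatch concerns that one adjusted contrast, and descriptive changes remain comparable.
- **That small arms make baseline imbalance a serious added problem.** Both models adjust for baseline, and nothing in the documents shows a material extra effect.

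**Conclusion.** The conflict holds as written. Following Part A SAP 16.3 and 16.4 leads to a log-ratio analysis, the protocol specifies an additive one, and no departure is declared. A log analysis of heart rate is not invalid in itself; the fault is that it contradicts the protocol silently and leaves the scale of a prespecified test open.

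The size is modest. It concerns the adjusted contrasts, confidence intervals and p-values of a secondary safety endpoint, in a part whose primary endpoints are pharmacokinetic. Under the assumptions above, significance verdicts rarely change, but the adjusted effect would not be given in bpm.

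One assumption remains. The Part A SAP is based on protocol version 1.0, which is not among the documents. The current protocol's list of amendments mentions no change to 9.4.7 or to the statistical methods in the synopsis, so the additive rule presumably already applied.

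**What to change.** In Part A SAP 16.3 and 16.4, add to the cross-reference that the model is additive with no log transformation: response equal to peak minus baseline in bpm, treatment as factor, untransformed pre-dose value as covariate, and LS mean differences in bpm with 95% confidence intervals.

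Part A is complete and its database has been locked and unblinded, so amending the SAP text is not enough. The sponsor should confirm which model was run.

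- **If additive:** say so in the clinical study report and note that the SAP wording was unclear.
- **If log-ratio:** rerun the two ANCOVAs additively, report those results in the clinical study report, and document the discrepancy there. Protocol 9.1 already requires deviations from the planned analysis to be described and justified.

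The cost is one sentence in two SAP sections, a check of the programs and, at most, two small models rerun on existing data. No new data are needed.
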